## **Comparative Effectiveness of Two Self-Assessment Tools: KIOS-Bipolar or eMoods: A Randomized, Open 52 Week Study for Persons with Bipolar Disorder**

**[name], [name], [name], [name], [name], [name].**

### **Abstract/Project Summary**

#### **A. Objective: *What we propose to do***

Bipolar disorder (BD) is a complex chronic illness characterized by recurrent, often dramatic mood changes. Self-management of BD is an important component of treatment, but is likewise complex and can be fraught with difficulties, including misunderstanding of the condition and a lack of self-awareness. Combined with the nationwide shortage of mental healthcare providers and the advent of the Affordable Healthcare Act, patients are assuming an increased role in understanding and managing their chronic conditions. At the same time, the emergence of mobile health and computational tools are engaging patients in self-management by enabling timely access to information and resources.

The goal of this project is to complete the development of a patient-centered software system and mobile app to assist in managing bipolar disorder. In Phase I, we developed a novel computational tool known as KIOS-Bipolar. Based on concepts from nonlinear systems (chaos) theory, KIOS-Bipolar tracks multiple interacting symptoms to determine the precise state of a BD patient. Once the patient's state is identified and the trajectory of the patient is established, KIOS-Bipolar produces advice specific to the patient's condition to help manage the course of the disease. To facilitate user convenience for the software, KIOS-Bipolar was converted to an online tool with mobile access. Twenty bipolar patients evaluated KIOS-Bipolar in a twelve week field trial. No technical problems with the software were observed and results showed that patients had significantly more reductions in symptom severity than increases. The development of this innovative tool to help patients self-manage BD has the potential to profoundly impact public health and achieve significant commercial success.

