**C. Hypotheses:**

a. Patients randomized to KIOS- Bipolar compared with those randomized to eMoods will have a higher proportion of time in remitted status, lower proportion in syndromal status (Manic, depressed, mixed) and higher

LFQ scores.

- b. Persistence with use of KIOS- Bipolar and eMoods will not differ. Persistence is defined as 1) the proportion of subjects who complete weekly scheduled use of the bipolar self-assessment scales and 2) completion of the 52 week self-assessment protocol.
- c. The proportion of on-time completion of assessments will not differ between groups.
- d. Subject satisfaction, assessed by qualitative questionnaires completed by subjects during and principally shortly following completion or discontinuation of the trial, will not differ between groups.
- e. LFQ subscales will be associated with superior outcomes for the KIOS-Bipolar group.
- f. Correlations between scores on items included in KIOS- Bipolar and similar items on the BISS SR and the BISS 42 will be conducted. Strength of association will be higher between KIOS- Bipolar and BISS comparisons than eMoods-BISS comparisons.
- g. Aggregate changes for the KIOS- Bipolar items and corresponding eMoods items will indicate greater proportions of decreased scores for KIOS- Bipolar

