#### **ASSESS KIOS-BIPOLAR OR eMOODS:**

- a. At the beginning of the study subjects will be provided preformatted evaluation sheets and will be encouraged to note observations regarding ease/benefits of use, impediments to use, and suggestions for additional features that would enhance the utility of KIOS-Bipolar or eMoods for sustained health.
- b. We will ask the subjects to estimate how completing the KIOS-Bipolar /eMoods assessments contributed to their self-awareness, attitude, and overall sense of satisfaction with their health status.
- c. We will assess the sensitivity of KIOS-Bipolar to identify improving or worsening by comparing the concordance between subject-assessed items with staff -administered BISS items that address similar symptoms.

**Plan of analysis:** The primary aims of the analyses are to investigate patterns of adherence and attrition. The term adherence refers to the extent to which participants follow the weekly completion of KIOS-Bipolar's eight pivotal symptoms of bipolar disorder. Adherence will be measured through such usage indicators as the proportion of weeks completed on time, the proportion completed only with follow-up prompts, and the number of weeks not submitted. Proportions of stable trajectories or improving trajectories are of primary interest. With  $n=90$  subjects (which allows for as many as 30 of the enrolled 120 subjects to have met some criterion for early termination) in the study we will be able to estimate any proportion within 0.10 with 95% confidence. For proportions larger than 0.9 we will be 95% confident we are within 0.06 of the true proportion. For a trajectory neither improving nor degrading there should be a 0.5 proportion

UTHSCSA tracking number: HSC20150321H

of each. For any hypothesis test for a proportion improving or degrading, i.e. not 0.5, we have 0.80 power at two tail significance of 0.05 to detect 0.65 different from 0.5 with n=90 subjects. For subgroups of patients with n=45 we can detect 0.71 different from 0.5 and with n=30 we can detect 0.74 different from 0.5. When comparing proportions of two subgroups of subjects, we will be 95% confident that the difference in proportions of the two subgroups is less than 0.25 for subgroups of n=30 and smaller than 0.20 for subgroups of size 40. If the proportions are larger than 0.9 (i.e. less variable), then we will be 95% confident that the difference in proportions of two subgroups with n=30(45) is less than 0.15 (0.12).

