Assumptions needed for each analysis will be examined to assure they are reasonably well met and the conclusions are valid. End of study overall improvement or not for each measure can be analyzed with logistic regression using covariates and predictors of interest. By focusing analyses on proportions and changes in trajectories, each subject will serve as their own control and trends in improved scores, symptoms and behavior may be identified.

Initially, we will also assess the effects of site, ethnicity, and bipolar disorder subtype (BD I, BD II), but none of these factors will be retained in the final model if they are not shown to be significant moderating factors.

The rate of dropout at any given time will be modeled through logistic regression models, with health, socioeconomic, and treatment factors as explanatory variables. *The impact of quality of life on dropout will be assessed similarly.*

**Outcome Measures from KIOS Analytics:** Knowledge Base performance metrics will be computed to measure the effectiveness of the content provided to patients. These metrics take several forms and are based on changes in the symptom scores for all subjects in the field trial (see Phase I Final Report). Changes in the symptom scores provide a global measure of efficacy. Each of these measures can be computed as a function of changes, either over the course of the entire field trial or at each incremental assessment. This latter approach will provide a measure of effectiveness over time. Other KIOS analytic methods will reveal which specific content in the knowledge base needs improvement. Behavioral frequency analysis will show which patient states are entered most frequently. Behavioral transition analysis will show which conditions are precedents to undesirable states.

**Implementation of Clinical Trial Results into Final Product:** The results of the randomized trial will be used to make further refinements to KIOS-Bipolar. The KIOS-generated results will be used to guide changes to the knowledge base. Suggestions about additional features will be considered in development of the commercialization plans.

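### Hypothesis g counts falling item scores as benefit, so staying well earns nothing and, if changes are counted week to week, the sicker arm can come out ahead

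*Combined protocol and SAP*

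**What the plan says.** Section C, hypothesis g: "Aggregate changes for the KIOS- Bipolar items and corresponding eMoods items will indicate greater proportions of decreased scores for KIOS- Bipolar". The hypothesis does not say over what interval a change is taken, what the denominator is, how unchanged scores count, or whether baseline is adjusted for.

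The only text on the interval is the paragraph on outcome measures from KIOS Analytics, within the plan of analysis. It says "Changes in the symptom scores provide a global measure of efficacy", and that the measures can be computed "either over the course of the entire field trial or at each incremental assessment". Of the second option it says: "This latter approach will provide a measure of effectiveness over time".

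Three other places bear on the reading:
- The plan of analysis says "Proportions of stable trajectories or improving trajectories are of primary interest", then sets a benchmark: "For a trajectory neither improving nor degrading there should be a 0.5 proportion" of each. That split leaves no place for unchanged scores.
- The project summary reports the Phase I field trial as a count of direction: "results showed that patients had significantly more reductions in symptom severity than increases".
- Hypothesis a predicts that KIOS-Bipolar patients "will have a higher proportion of time in remitted status".

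The inclusion and exclusion criteria set no minimum symptom score. Participants must already have taken a mood stabilizer or second generation antipsychotic for at least 4 weeks, so patients who are well can enrol.

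**The concern.** A count of the direction of change carries no information about level. An item at its minimum cannot decrease, so an item that stays there all year contributes either zero decreases or nothing. An item stuck at its maximum all year gets the same result.

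With week-to-week counting there is a second problem. Every relapse creates the opportunity for later decreases, and a recovery in four steps yields four decreases where an abrupt one yields one. A tool that prevented relapse or shortened episodes could then do well on hypothesis a and badly on g. A result in favour of g could be reported as efficacy when it reflects more relapses or slower recovery.

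**Working it through.** **The plan's own figure.** None is given for hypothesis g. The nearest is 0.80 power to detect 0.65 against 0.5 with n=90, two-sided 0.05. Check: 0.15/√(0.25/90) = 2.846; 2.846 − 1.960 = 0.886; power Φ(0.886) = 0.81. It reproduces, but it is a one-sample test in which every subject either improves or degrades, so it does not bear on g.

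**Inputs.** From the documents: weekly entries for 52 weeks, and no entry minimum. Assumed: items scored 0–4. That is the BISS item range; neither app's range is stated. All transition risks below are assumptions and show direction only.

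**Step 1: single-item paths.** There are 53 weekly scores and so 52 changes. Every path starts and ends at the same score.

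| Path | Down / up | Down ÷ 52 | Down ÷ (down + up) | Mean score |
|---|---|---|---|---|
| At 0 all year | 0 / 0 | 0 | undefined | 0 |
| At 4 all year | 0 / 0 | 0 | undefined | 4 |
| One episode, fast (0,4,0) | 1 / 1 | 1.9% | 50% | 4/53 = 0.075 |
| One episode, slow (0,4,3,2,1,0) | 4 / 1 | 7.7% | 80% | 10/53 = 0.189 |
| Three fast episodes | 3 / 3 | 5.8% | 50% | 12/53 = 0.226 |
| Three slow episodes | 12 / 3 | 23.1% | 80% | 30/53 = 0.566 |
| One episode, gradual onset and recovery | 4 / 4 | 7.7% | 50% | 16/53 = 0.302 |

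For a patient who enters at 4 and recovers once, fast gives 1/52 and slow gives 4/52. Both give 100% of non-zero changes, and both count as one decrease from baseline to end.

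**Step 2: whole arms.** Let p(t) be the probabilities of scores 0–4 at week t, with p(t+1) = p(t)P for transition matrix P. Expected weekly decreases are the sum over t and score i of p(t,i) × P(move down from i), divided by 52 for the all-changes version, or compared with the matching sum for increases. Baseline-to-end uses P to the power 52.

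- Scenario A, recovery speed: half start at 0 and half at 4; abrupt onset (0 to 4) with weekly chance 0.03; weekly chance of improving 0.5, by one step (slow) or straight to 0 (fast).
- Scenario B, relapse rate: one-step moves; weekly worsening 0.15 (sicker) or 0.03 (better); improvement 0.30; baseline shares 0.30, 0.25, 0.20, 0.15, 0.10 at scores 0–4.
- Scenario C, baseline only: worsening 0.05 and improvement 0.20 in both arms; baseline shares 0.1, 0.2, 0.3, 0.2, 0.2 (ill start) or 0.6, 0.2, 0.1, 0.05, 0.05 (well start).

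| Measure | A: slow vs fast | B: sicker vs better | C: ill vs well start |
|---|---|---|---|
| Mean score | 0.61 vs 0.29 | 0.95 vs 0.29 | 0.76 vs 0.43 |
| Weekly decreases, all changes | 0.120 vs 0.036 | 0.156 vs 0.057 | 0.084 vs 0.058 |
| Weekly decreases, non-zero changes | 0.84 vs 0.57 | 0.52 vs 0.65 | 0.63 vs 0.54 |
| Baseline-to-end decrease, all patients | 0.48 vs 0.47 | 0.52 vs 0.67 | 0.83 vs 0.34 |
| Baseline-to-end decrease, unchanged excluded | 0.83 vs 0.94 | 0.70 vs 0.95 | 0.95 vs 0.68 |

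The first figure in each pair is the arm with the worse mean score. Week-to-week counting over all changes favours that arm in A and B. Over non-zero changes it does so in A but not in B. Baseline-to-end counting is practically tied in A with all patients counted, and otherwise favours the better arm in A and B. In C, where nothing differs but baseline severity, the arm that starts sicker scores higher on all four.

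**The case against.** The strongest reply is that the reversal depends on the reading. The Phase I summary and the 0.5 benchmark both suggest decreases set against increases, and in scenario B that version ranks the arms correctly. Baseline-to-end counting does so too. The 80% figure for slow recovery also needs abrupt onset: with gradual onset and gradual recovery it is 50%. The KIOS Analytics paragraph does not say its metrics are counts of direction. It refers to a Phase I report not included here, and serves partly to refine the knowledge base. Stability is named as of primary interest in the plan of analysis, hypothesis a credits remission directly, and g is the last of seven hypotheses in a plan whose stated primary aims are adherence and attrition.

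Most of this stands, and it rules out several stronger inferences a reader might draw:
- That g generally favours the sicker arm, or that hypotheses a and g must conflict. Three of the four readings rank the arms correctly in scenario B.
- That fast recovery always scores worse than slow. That is confined to week-to-week counting.
- That the ranking always runs against mean score. One slow episode (4/52, mean 0.19) against three fast ones (3/52, mean 0.23) ranks correctly, and also on non-zero changes (80% against 50%).
- That no remitted patient can record a decrease. The documents do not define remission as zero on every item, so the floor binds items at their minimum, not every remitted patient.

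What the reply does not remove is that g itself uses the direction of change, fixes no reading, and carries over no rule for stability. The only text on the interval permits the version that can reverse and calls it a measure of effectiveness.

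**Conclusion.** The point holds in this form. Under any reading, an item that stays at its minimum earns no credit or drops out. Under week-to-week counting, more relapses can raise the proportion of decreases over all changes, and slower stepwise recovery after abrupt onset can raise it with or without unchanged scores in the denominator. In the illustrations the sicker arm led by 0.120 to 0.036 and 0.156 to 0.057 on all changes, and by 0.84 to 0.57 on non-zero changes in the recovery-speed case. Baseline-to-end counting does not reward slower recovery, but it keeps the floor problem and depends on baseline severity. Randomisation makes baseline imbalance a matter of chance, but g includes no adjustment for it.

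The sizes rest on an assumed 0–4 range and assumed transition risks; only the direction should be carried away. The consequence is limited by hypothesis a and by g's place in the plan. It is still more than missing detail, because an analyst who follows a permitted reading could report the wrong direction as efficacy.

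**What to change.** In hypothesis g and the KIOS Analytics paragraph, stop using the count of decreased scores as a between-arm efficacy measure. Compare the arms on level: BISS-42 depression, mania, irritability and anxiety scores, with the matching BISS-Self scores, at weeks 8, 16, 24, 32, 40 and 52, adjusted for the week-0 score and analysed by randomised arm. Table 1 already schedules both scales at those visits.

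A mean of the app items themselves would not serve. Neither app's score range is stated, and participants with technical problems may switch apps, so one person's mean could mix instruments. The BISS avoids both problems.

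Keep counts of increases, decreases and unchanged scores within each app as description, with the share of items at the floor, and do not call the assessment-to-assessment count a measure of effectiveness.

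The cost is rewording one hypothesis and one paragraph, with no new data. The downside is small: the comparison rests on six follow-up visits rather than weekly entries, and it is less directly comparable with the Phase I summary of reductions against increases, which can still be shown.

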**D. Measures of clinical status – BISS and K-B**

The BISS (Bipolar Inventory of Symptoms Scale) is a 42 item, structured, clinician-administered rating scale that has demonstrated good sensitivity to change across the life span. Unlike traditional scales, which focused on inpatient samples, the BISS was developed with a focus on outpatients. The scale yields an overall severity of illness score and five domain scores (for manic, depressive, anxious, irritable, and psychotic elements, with the latter established in exploratory factor analyses). The psychometric characteristics of the BISS were established in studies on over 400 patients in all clinical states of BD. Table 2 provides the BISS clinician-rated items from which the KIOS-BIPOLAR items were derived and the KIOS-BIPOLAR questions that the patients will answer. The final design for the user input will be determined in Aim 1.1.

**Table 2. BISS Item and Corresponding KIOS-BIPOLAR Questionnaire**

BISS Item	KIOS-BIPOLAR Question
Affective Lability	Have your emotions shifted fairly suddenly at times?
Sadness	Have you felt depressed, sad or down?
Irritability	Have you felt easily irritated, angry or resentful?
Pessimism	Have you been discouraged, pessimistic or felt hopeless?
Anxiousness	Have you felt tense or anxious?
Less Need for Sleep	Were there nights you needed less sleep than usual?
Psychomotor Slowing	Have you felt slowed down?
Energetic	Have you had more energy than usual to do things?

**Software:** Subjects assigned to KIOS-Bipolar will have the app loaded onto their preferred device. The program is available for iPhone and Android devices, and accessible on a pc. The research coordinator will demonstrate the KIOS-Bipolar operation with the subject and ask the subject if he/she has any questions about the procedures of the trial. A phone number and email address will be provided to allow the subject to make contact if any question arises after leaving the clinic. The data entry procedure will take less than 5 minutes per session, with most subjects completing their entries in 2 minutes.

For participants who have been randomized to the eMoods App an additional procedure will occur. After each completed weekly entry on eMoods, the participant will have the option to email the results to the Research Coordinator weekly or postpone sending data until their scheduled research visit.

The subject will be told that an email, text, or push notification reminder will be sent one day after a missed scheduled assessment. The participants phone number will be shared with a third-party (Twilio) solely for the purpose of reminding the participant to complete their questionnaire. This information will only be used for the administration of the push notification and will be kept strictly confidential. The participant will not have the option to opt out of the notification. For participants randomized to KIOS-Bipolar, a text message reminder will be sent one day after a missed scheduled assessment. The participant's phone number will be added to New Patient section in KIOS-Bipolar.

It should be noted that the Summary Statement contained a criticism that email reminders prior to expected assessment days would be a direct intervention that confounds weekly reporting adherence. Because the reminder will be sent *after* the scheduled assessment day, we are still able to judge adherence to the study schedule; the response to the notifications will provide a relevant secondary outcome measure. In addition, many subjects in the Field Trial requested this feature, which will almost certainly be included as an option in the commercialized version of KIOS-Bipolar.

Study participants assigned to eMoods will also have the software downloaded on their device (Either Android phone or computer) and the procedure of demonstrating the software and providing contact information described above will be followed. In the case that the IOS version of eMoods is not available by the time the study begins, the randomization of subjects will be stratified by device to ensure equal representation in the treatment groups.

Participation in the study will not impact the patient's routine clinical care for his/her bipolar condition. However, some subjects may want to discuss their KIOS-Bipolar or eMoods experience with their psychiatrist and/or psychologist, and will be permitted to do so.

Participants randomized to their assigned group who are unable to complete their weekly entries based on the following criteria: technical difficulties completing the weekly entry, difficulty emailing data to Research Coordinator (for eMoods group), and any other technical issues that may arise throughout the course of the study will have the option to switch to the other group. The participants who have been switched to the other group will have to complete a BISS self-report form along with a weekly entry from the newly assigned group.

Focus group(s): There will be an addition of one group at approximately Week 8. The group will have 10 participants and the focus of the group will be related to participants experience with mood charting. Recruitment for group 1 will consist of participants who are not currently enrolled in the 52-week comparative study. One half of the group will be participants who have experienced with mood charting and the other half will be participants with no prior mood charting experience. The focus of the first group will consist of the participants experience with mood charts as well as polling the participants on their preferences for logging in, graphs, and other software features.

Additionally, there will be a focus group at approximately Week 16. The focus group will consist of 10 participants who are currently randomized to the KIOS-Bipolar app. The focus of the second group will be related to their experience using the KIOS-Bipolar app along with suggestions for improvements. The participants will be polled on their preferences related to but not limited to logging in, graphs, advice, as well as other KIOS-Bipolar software features.

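### eMoods users alone may hold entries until the next visit, so the one-day reminder cannot be shown to be applied alike in the two arms

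*Combined protocol and SAP*

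**What the plan says.** The Software paragraphs of Section D set out two rules.

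- **Data transfer.** An extra step applies to eMoods participants only. Once a week's entry has been made, the rule is that "the participant will have the option to email the results to the Research Coordinator weekly or postpone sending data until their scheduled research visit". No such step is described for KIOS-Bipolar.
- **Reminders.** Subjects are told that "an email, text, or push notification reminder will be sent one day after a missed scheduled assessment"; no arm is named. Phone numbers go to a third-party messaging service for this purpose and opting out is not allowed, again with no arm named. A separate sentence reads "For participants randomized to KIOS-Bipolar, a text message reminder will be sent one day after a missed scheduled assessment", and the number is entered in the KIOS-Bipolar system.

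Three further places use the result.

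- Section D defends reminders as coming after the scheduled day, and adds that "the response to the notifications will provide a relevant secondary outcome measure".
- The Plan of analysis says "The primary aims of the analyses are to investigate patterns of adherence and attrition". It measures adherence by indicators such as "the proportion of weeks completed on time, the proportion completed only with follow-up prompts, and the number of weeks not submitted". Its adherence definition names only KIOS-Bipolar, although objective b and Section C show that weekly completion of both tools is of interest.
- Section C hypothesises no difference between arms in persistence, which includes weekly completion (b), or in on-time completion (c).

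Section D also counts "difficulty emailing data to Research Coordinator (for eMoods group") among the reasons a participant may be unable to complete weekly entries and may switch groups.

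**The concern.** A reminder due one day after a miss needs someone, or some system, to know by then that the entry was missed. If an eMoods user is holding data, a missed week and a completed but unsent week look the same through the data route the protocol describes. There are then two possibilities. If no reminder goes out, real misses are left unprompted. If one goes out regardless, people who already completed are reminded wrongly.

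Because only one arm may hold data, either outcome falls on that arm alone. A difference between arms in prompted completion or in response to reminders, or the absence of one, could then reflect how data were sent rather than the tool. Reminders also act on behaviour: a user who is not prompted may never complete the week late, which can lower weekly completion under hypothesis b.

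The two errors are not equally repairable. Wrong reminders can be removed in analysis if entries carry dates. A reminder that was never sent cannot be reconstructed.

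**Working it through.** The plan states no figure on this point, so there is none to reproduce. The check has a part that uses only the visit schedule and a part that rests on assumed values.

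**From the documents.** Weekly entries fall in weeks 1 to 52. Post-baseline visits are at weeks 8, 16, 24, 32, 40 and 52 (objective f; Table 1). The gaps are 8, 8, 8, 8, 8 and 12 weeks. I treat an entry in a visit week as having no wait.

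- Entries waiting more than zero weeks, for a user who always holds: 5 × 7 + 11 = 46 of 52 (88.5%).
- Total wait: 5 × (7 + 6 + … + 0) + (11 + 10 + … + 0) = 5 × 28 + 66 = 206 weeks. Mean: 206/52 = 3.96 weeks. Maximum: 11 weeks.

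This is a ceiling per user. For a week that is emailed promptly, status is known. An email that does not arrive still does not prove a missed entry.

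**Illustration on assumed values.** The documents give none of these. Let q be the share of eMoods users who always hold, p the on-time proportion and r the proportion of true misses that a reminder recovers. I take p and r as equal in both arms and in holders and others. Central values are p = 0.8 and r = 0.5, with q from 0.2 to 0.3.

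Share of eMoods arm-weeks with unknown status: u = q × 46/52 = 0.177 to 0.265.

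*If no reminder is sent for unknown weeks:*

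- Misses left unprompted: (1 − p)u = 0.2 × 0.177 to 0.2 × 0.265 = 3.5% to 5.3% of arm-weeks. The range is 1.8% (p = 0.9, q = 0.2) to 10.6% (p = 0.6, q = 0.3).
- Prompted completion, KIOS-Bipolar: (1 − p)r = 10.0%.
- Prompted completion, eMoods: (1 − p)r(1 − u) = 8.2% to 7.3%.
- Gap: (1 − p)ru = 1.8 to 2.7 points. With p = 0.8, the range is 1.1 (r = 0.3, q = 0.2) to 3.7 (r = 0.7, q = 0.3). If late entries count, total completion differs by the same amount, which is the link to hypothesis b.
- Over all possible q at the central p and r, the gap runs from 0 (nobody holds) to 0.10 × 46/52 = 8.8 points (everyone holds).

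*If a reminder is sent for every unknown week:*

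- Wrong reminders: pu = 14% to 21% of arm-weeks. The range is 11% (p = 0.6, q = 0.2) to 24% (p = 0.9, q = 0.3).
- Apparent response per reminder: (1 − p)r / [(1 − p) + pu] = 0.10/0.342 to 0.10/0.412 = 29% to 24%, against a true 50%. This distortion goes away if reminders for entries already made are removed by entry date.

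**The case against.** The strongest reply has four parts.

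**Silence is not proof.** The protocol does not say how a missed eMoods entry is detected, but it does not rule out a method. A reminder generated inside eMoods or a data feed would remove the problem. This stands, and it is why the claim is limited to what can be shown. A reader might infer that the reminder rule is impossible to apply alike; the documents do not support that.

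**The channel may be the same.** A reader might infer from the separate KIOS-Bipolar sentence that the arms get different reminder channels. The sentences on the messaging service and on no opt-out name no arm, and they fit phone-based reminders in both. That weakens the channel point. It does not touch detection: a means of sending a reminder does not show when one is due.

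**No between-arm test of these two measures is planned.** Neither response to notifications nor prompted completion is expressly compared by arm, and the adherence definition names KIOS-Bipolar only. This stands, so those measures are exposed only if compared. Hypothesis b is a stated between-arm hypothesis, though, and unequal prompting can move weekly completion. The defence that reminders follow the scheduled day protects on-time status, not late completion.

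**The effect is small against the plan's precision.** The Plan of analysis gives 0.10 for one proportion and 0.20 to 0.25 for differences between subgroups of 40 and 30. The illustrated gap of 1.8 to 2.7 points is well below these. The comparison is rough, because those figures are for proportions of subjects and mine are for person-weeks, but the bias may indeed be small.

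**Conclusion.** The concern holds in a limited form. Two rules in the same part of Section D do not fit together for held eMoods weeks, and no described procedure joins them. Equal application of the reminder therefore cannot be shown.

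The only figures fixed by the documents are the ceiling of 46 of 52 entries per always-holding user and the longest wait of 11 weeks. The rest depends on assumed rates of holding, on-time completion and recovery. The size of any bias is unknown and may be small; it is zero if nobody holds and emails arrive on time.

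A reader might also infer that on-time completion (hypothesis c) is biased. The documents do not support that. Its wording concerns completion, not receipt, so it is exposed only if eMoods weeks are scored by the date data arrived. The protocol does not say which date is used.

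The point deserves a protocol change rather than an analysis note, because unsent reminders cannot be recovered and the change is cheap.

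**What to change.** 1. Word the adherence definition in the Plan of analysis for both tools. Score each week by the date the entry was made in the tool, not the date it was received, and confirm that eMoods exports carry that date.
2. State how a missed eMoods entry is identified. Use one reminder trigger and one channel that work in both arms without relying on held data. Options are a brief weekly confirmation of completion, or weekly sending encouraged as the default but not required. A confirmation request is itself a prompt, so it should come after the scheduled day and be identical in both arms. Log every reminder.
3. Report entries made on time but sent late, and reminders sent for entries already made. Where next-day status stays unknown, report prompted completion and response to reminders descriptively by arm with no between-arm conclusion, and note unequal prompting as a limit on hypothesis b.

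The cost is protocol wording, a reminder log and, if weekly sending is encouraged, a small added task for eMoods users. Making weekly sending compulsory is not advised. It would burden one arm on the outcome being measured, could add to switching since emailing difficulty is a permitted ground, and an unsent email would still not prove a missed entry.
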